## **7.4 Procedures to Encourage Continued Trial Participation**

In all cases of impending IMP discontinuation or consent withdrawal, investigators will be instructed to meet and discuss (without undue coercion) with the subject their options of continuing in the trial, preferably on therapy. The investigator should ensure understanding and documentation of the reasons for the subject's desire to withdraw consent.

## **7.5 Lost to Follow up**

A subject will be considered lost to follow-up if he or she repeatedly fails to return for scheduled visits and is unable to be contacted by the trial site personnel.

The following actions must be taken if a subject fails to return to the site for a required trial visit:

- The site personnel must attempt to contact the subject and reschedule the missed visit as soon as possible and counsel the subject on the importance of maintaining the assigned visit schedule and ascertain whether or not the subject wishes to and/or should continue in the trial
- Before a subject is deemed lost to follow up, the investigator or designee must make every effort to regain contact with the subject (where possible, 3 telephone calls and a certified letter to the subject's last known mailing address or local equivalent methods). These contact attempts should be documented in the subject's medical record
- Should the subject continue to be unreachable, he/she will be considered to have withdrawn from the trial

## **8 TRIAL ASSESSMENTS AND PROCEDURES**

Trial procedures and their timing are summarized in the Schedule of Assessments ([Table 2](#) and [Table 3](#)). Protocol waivers or exemptions are not allowed.

Immediate safety concerns should be discussed with the medical monitor immediately upon occurrence or awareness to determine if the subject should continue or discontinue IMP.

Adherence to the trial design requirements, including those specified in the Schedule of Assessments ([Table 2](#) and [Table 3](#)), is essential and required for trial conduct.

## **8.1 Screening/Baseline Assessments**

The timing for all screening/baseline assessments is provided in the Schedule of Assessments ([Table 2](#) and [Table 3](#)).

A review of all inclusion and exclusion criteria will occur at Visit 1 (screening/baseline visit) to confirm that potential subjects meet all eligibility criteria. The investigator will maintain a screening log to record details of all subjects screened and to confirm eligibility or record reasons for screening failure, as applicable. As there may be a delay in obtaining all relevant assessments (eg, laboratory results) prior to subject enrollment in Trial CVL-865-SZ-002, if any data from assessments are obtained after enrollment and indicate the subject would not be eligible to continue in the extension trial, the medical monitor should be contacted.

Subjects will continue to record the presence or absence of all seizure types experienced daily in the eDiary from Visit 1 through Visit 17 (end of follow-up period). Site personnel should classify the seizure type based upon the description provided by the subject in the eDiary and, if needed, via further discussion with the subject. If a new seizure type occurs during the trial, the seizure category will be evaluated by the investigator and, if confirmed to be new, and not reported previously, it will be submitted to TESC for review. If seizures do not occur on any given day, lack of seizures is also recorded. Subjects will also record any use of benzodiazepines and dosing with CVL-865 in the eDiary.

## **8.2 Efficacy Assessments**

### **8.2.1 Seizure Frequency and Type (eDiary)**

Subjects will record details regarding their seizures (frequency and type) in an eDiary. Any benzodiazepine use will also be recorded in the diary.

Seizure frequency and type will be assessed based on information recorded by the subject in the eDiary (see [Section 8.1](#)).

### **8.2.2 Patient Global Impression of Change**

The self-report measure Patient Global Impression of Change (PGI-C) reflects a patient's belief about the efficacy of treatment. It is a 7-point scale depicting a patient's rating of overall improvement. Patients rate their change as "very much improved," "much

improved,” “minimally improved,” “no change,” “minimally worse,” “much worse,” or “very much worse.”

### **8.2.3 Clinical Global Impression-Severity Scale**

The Clinical Global Impression – Severity (CGI-S) is an observer-rated scale that will be used to measure symptom severity. It is important to note that the observer or rater will provide their assessment of the subject’s symptoms at the time of the current visit.

To perform this assessment, the investigator (or designee) will answer the following question: “Considering your total clinical experience with this particular population, how ill is the subject at this time?” Response choices are 0 = not assessed; 1 = normal, not at all ill; 2 = borderline ill; 3 = mildly ill; 4 = moderately ill; 5 = markedly ill; 6 = severely ill; and 7 = among the most extremely ill subjects.

## **8.3 Safety Assessments**

Planned time points for all safety assessments are provided in the Schedule of Assessments ([Table 2](#) and [Table 3](#)).

For the assessments described below, when multiple procedures are scheduled on the same visit, the following chronology of events should be adhered to, where possible:

- ECGs, obtain prior to vital sign measurements
- Blood pressure/heart rate, obtain prior to procurement of blood specimens
- Blood specimen collection
- Other procedures: all other procedures may be obtained before or after blood specimen collection

### **8.3.1 Physical and Neurological Examinations**

A complete physical examination will consist of measurement of weight and a review of the following body systems: head, ears, eyes, nose, mouth, skin, heart and lung examinations, lymph nodes, gastrointestinal, genitourinary, and musculoskeletal systems. If the investigator/designee is unable to perform a genitourinary examination, special attention will be given to the genitourinary medical history. A prior record (within 12 months of enrolling into CVL-865-SZ-001) of a recent genitourinary examination from a gynecologist or family doctor can substitute for a genitourinary examination.

A full neurological examination will include an assessment of the subject’s mental status (level of consciousness, orientation, speech, memory, etc.), cranial nerves, motor (muscle appearance, tone, strength and reflexes), sensation (including Romberg sign), coordination, and gait.

The following guidelines will aid in the standardization of body weight measurements:

- The same scale should be used to weigh a given subject each time, if possible
- Scales should be calibrated and reliable; scales should be at zero just prior to each subject's weigh-in session
- A subject should void prior to being weighed and be minimally clothed (ie, no shoes or heavy overgarments)
- To the best of the subject's and site personnel's ability, weight should be recorded before a subject's meal and at approximately the same time at each visit

The investigator (or designee) is responsible for performing the physical and neurological examinations. If the appointed designee is to perform these examinations, he or she must be permitted by local regulations and his or her name must be included on the delegation of authority log. Whenever possible, the same individual should perform all physical and neurological examinations.

Any condition present at the post-treatment physical and neurological examinations that was not present at the baseline examination should be documented as an AE and followed to a satisfactory conclusion.

### **8.3.2     *Vital Sign Measurements***

Vital sign measurements will include body temperature, respiratory rate, systolic blood pressure, diastolic blood pressure, and heart rate.

Vital signs will be measured with the subject in a sitting/semi-recumbent position after 5 minutes rest.

A properly sized and calibrated blood pressure cuff will be used to measure blood pressure each time. The use of an automated device for measuring blood pressure and heart rate is acceptable, although, when done manually, heart rate will be measured in the brachial/radial artery for at least 30 seconds. When the timing of these measurements coincides with a blood collection, blood pressure and heart rate should be obtained prior to the nominal time of the blood collection.

Body temperature will be measured with either an oral (temperature taken at floor of the mouth) or tympanic thermometer. The same method (ie, oral or tympanic) must be used for all measurements for each individual subject and should be the same for all subjects.

Any clinically relevant changes occurring during the trial will be recorded in the AE section of the eCRF.

### **8.3.3     *Electrocardiograms***

Electrocardiogram recordings will be obtained after the subject has been at rest for at least 5 minutes. Additional ECGs may be obtained at the investigator's discretion and should always be obtained in the event of early termination. The ECG results will be evaluated at the investigational site to determine the subject's eligibility and to monitor safety during the trial. The investigator (or qualified designee) will review, sign, and date each ECG reading, noting whether or not any abnormal results are of clinical significance. Any clinically relevant changes occurring during the trial will be recorded in the AE section of the eCRF. The ECG will be repeated if any results are considered to be clinically significant. A central ECG service will be used for reading all ECGs in order to standardize interpretations for the safety analysis.

### **8.3.4     *Clinical Safety Laboratory Assessments***

See [Section 10.2](#) (Appendix 2) for the list of clinical laboratory tests to be performed and to the Schedule of Assessments ([Table 2](#) and [Table 3](#)) for the timing and frequency.

The investigator must review the laboratory report, document this review, and record any clinically relevant changes occurring during the trial in the AE section of the eCRF. The laboratory reports must be filed with the source documents.

All laboratory tests with values considered clinically significantly abnormal during participation in the trial should be repeated until the values return to normal or baseline or are no longer considered clinically significant by the investigator or medical monitor.

If such values do not return to normal/baseline within a period of time judged reasonable by the investigator, the etiology should be identified and the medical monitor notified.

All protocol-required laboratory assessments, as defined in [Section 10.2](#) (Appendix 2), must be conducted in accordance with the laboratory manual and the Schedule of Assessments ([Table 2](#) and [Table 3](#)).

### **8.3.5     *Modified Clinical Institute Withdrawal Assessment Scale – Benzodiazepines***

The modified Clinical Institute Withdrawal Assessment Scale – Benzodiazepines (mCIWA-B) is a sensitive instrument to measure withdrawal under conditions where there is a taper of medication (rather than abrupt discontinuation). It consists of 17 items that monitor the type and severity of benzodiazepine withdrawal symptoms such as irritability, fatigue, appetite, and sleeplessness ([Busto et al, 1989](#)). The clinician-observed assessments of sweating, restlessness (pacing), and tremor that are included in the overall version have been removed from this modified version. The total score ranges from 1 to 68 with higher scores indicating more severe withdrawal.

### **8.3.6     *Suicidal Ideation and Behavior Risk Monitoring***

Suicidality will be monitored during the trial using the C-SSRS. This semi-structured interview was originally developed to evaluate the link between antidepressants and suicidal behavior and ideation in youth and adverse events from pediatric clinical trials (Posner et al, 2011). It was designed to quantify the severity of suicidal ideation and behavior. Trial personnel administering the C-SSRS must have completed the appropriate training and have valid certification. Training on the scale will be provided via the sponsor or designee.

The “Since Last Visit” C-SSRS form will be completed at all visits. The investigator will review the results of the “Since Last Visit” C-SSRS during the trial to determine whether it is safe for the subject to continue in the trial. If a subject demonstrates potential suicidal ideation associated with actual intent or method or plan as indicated by “YES” answers on item 4 or 5 of the C-SSRS, the investigator will need to evaluate whether a risk assessment by a qualified mental health professional (MHP, or the investigator alone if the investigator is a qualified MHP) is needed and whether the subject should continue in the trial or be discontinued.

## **8.4     *Adverse Events and Serious Adverse Events***

The definitions of an AE or SAE can be found in [Section 10.3](#) (Appendix 3).

Adverse events will be reported by the subject (or, when appropriate, by a caregiver, surrogate, or the subject’s legally authorized representative).

The investigator and any qualified designees are responsible for detecting, documenting, and recording events that meet the definition of an AE or SAE and remain responsible for following up AEs that are serious, considered related to the IMP or trial procedures, or that caused the subject to discontinue IMP (see [Section 7](#))

### **8.4.1     *Time Period and Frequency for Collecting AE and SAE Information***

All AEs and SAEs will be collected from the signing of the ICF until the follow-up visit (Visit 17 at Day 428) at the time points specified in the Schedule of Assessments ([Table 2](#) and [Table 3](#)).

All SAEs will be recorded and reported to the medical monitor immediately and under no circumstance should this exceed 24 hours, as indicated in [Section 10.3](#) (Appendix 3). The investigator will submit any updated SAE data to the medical monitor within 24 hours of it being available.

Investigators are not obligated to actively seek AE or SAE after conclusion of the trial participation. However, if the investigator learns of any SAE, including a death, at any time after a subject has been discharged from the trial, and he/she considers the event to

be reasonably related to the IMP or trial participation, the investigator must promptly notify the sponsor.

#### **8.4.2     *Method of Detecting AEs and SAEs***

The method of recording, evaluating, and assessing causality of AE and SAE and the procedures for completing and transmitting SAE reports are provided in [Section 10.3](#) (Appendix 3).

Care will be taken not to introduce bias when detecting AEs and/or SAEs. Open-ended and nonleading verbal questioning of the subject is the preferred method to inquire about AE occurrences.

#### **8.4.3     *Follow-up of AEs and SAEs***

After the initial AE/SAE report, the investigator is required to proactively follow each subject at subsequent visits/contacts. All SAEs will be followed until resolution, stabilization, the event is otherwise explained, or the subject is lost to follow-up (as defined in [Section 7.5](#)). Further information on follow-up procedures is given in [Section 10.3](#) (Appendix 3).

#### **8.4.4     *Regulatory Reporting Requirements for SAEs***

Prompt notification by the investigator to the medical monitor of a SAE is essential so that legal obligations and ethical responsibilities towards the safety of subjects and the safety of an IMP under clinical investigation are met.

The sponsor has a legal responsibility to notify both the local regulatory authority and other regulatory agencies about the safety of an IMP under clinical investigation. The sponsor will comply with country-specific regulatory requirements relating to safety reporting to the regulatory authority, IRB/IEC, and investigators.

Investigator safety reports must be prepared for suspected unexpected serious adverse reactions according to local regulatory requirements and sponsor policy and forwarded to investigators as necessary.

An investigator who receives an investigator safety report describing a SAE or other specific safety information (eg, summary or listing of SAEs) from the sponsor will review, acknowledge, and then file it along with the Investigator's Brochure and will notify the IRB/IEC, if appropriate according to local requirements.

#### **8.4.5     *Pregnancy***

Details of all pregnancies in female subjects and female partners of male subjects will be collected after the start of IMP and until the final contact at Visit 17. At a minimum, monthly pregnancy tests will be completed throughout the trial for all women of

childbearing potential. During periods where monthly visits are not scheduled, female subjects can choose to visit the site for the test or complete the test via a remote option.

If a pregnancy is reported, the investigator should inform the medical monitor within 24 hours of learning of the pregnancy and should follow the procedures outlined in [Section 10.4](#) (Appendix 4).

Abnormal pregnancy outcomes (eg, spontaneous abortion, fetal death, stillbirth, congenital anomalies, ectopic pregnancy) are considered SAEs.

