#### Follow-up Period:

Follow-up telephone contact will be performed  $7\pm3$  days after the last dose of IMP. A Post-treatment Follow-up Visit will be made approximately 4 weeks after last dose of IMP.

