#### 4.4 Definition of Completed Subject

A subject is considered to have completed the trial if he/she has completed all phases of the trial including the last scheduled procedure (ie, Visit 17 assessments) as shown in the Schedules of Activities ([Table 2](#) and [Table 3](#)).

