#### 5.1 Inclusion Criteria

Subjects are eligible to be included in the trial only if all of the following criteria apply:

1.	Subjects who completed treatment in Trial CVL-865-SZ-001 (ie, subjects who completed Visit 4 of Trial CVL-865-SZ-001).
2.	A female subject of childbearing potential (see Section 10.4 , Appendix 4) who is sexually active with a nonsterilized male partner must agree to use a highly effective method of contraception (see Section 10.4 , Appendix 4) from signing of informed consent through 30 days post last dose. A male subject with a pregnant or a nonpregnant partner of childbearing potential must agree to use a condom during treatment and until the end of relevant systemic exposure in the male subject for 94 days following the last dose with IMP.
3.	Subjects who are capable of giving signed informed consent as described in Section 10.1.3 (Appendix 1)
4.	Subjects who are able, in the opinion of the investigator, to understand the nature of the trial and comply with protocol requirements, including the prescribed dosage regimens, scheduled visits, laboratory tests, and other trial procedures.

Abbreviations: BID = twice daily; ICF = informed consent form

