## **7.3 Individual Subject Discontinuation**

After treatment assignment, a subject may stop treatment permanently for a variety of reasons. Treatment discontinuations may be initiated by a subject who is not satisfied with treatment or may become medically necessary due to AEs, required treatment with a disallowed medication or therapy, or other issues, as determined by the investigator.

Subjects should begin the Taper Phase at the time the decision is made to discontinue. All Taper Phase and Post-treatment Follow-up procedures should be performed as indicated in the Schedules of Assessments ([Table 2](#) and [Table 3](#)). Under certain circumstances, when subjects leave the trial early, dosing with the taper medication or continuing with the taper phase medication may be inadvisable. The decision not to taper the subject is upon agreement from the medical monitor. If the taper will not be utilized, then all assessments required at Visit 17 should be conducted approximately 30 days following the last dose.

For subjects who early terminate prior to Day 15 (prior to the Maintenance Phase), an alternate taper scheme may be used. This includes subjects who sign consent for CVL-865-SZ-002 but who are then determined to not meet eligibility criteria.

A subject will discontinue IMP for the reasons listed below:

- Any of the following AESIs

- Hemoglobin <8 g/dL
- WBC count <2.5 × 10^9/L
- Neutrophil count <1.5 × 10^9/L
- Platelet count <100 × 10^9/L
- Female subjects who have a positive pregnancy test result during the trial
- Withdrawal of consent
- Investigator's discretion (eg, including failure to comply with trial procedures or dosing)

All subjects have the right to withdraw their consent from further participation in the trial at any time without prejudice. Subjects cannot withdraw consent for use of data already collected as part of the trial, but only for future participation. The investigator can also discontinue a subject's participation in the trial at any time if medically necessary. Unless the subject provides their written withdrawal of consent or there is other written documentation by the investigator confirming the subject's verbal intent to completely withdraw from the trial, subjects should be followed for all protocol-specified evaluations and assessments, if possible.

Complete withdrawal of consent requires a subject's refusal of ALL of the following methods of follow-up:

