#### **Collection of Pregnancy Information**

##### **Male subjects with partners who become pregnant**

- The investigator will attempt to collect pregnancy information on any male subject's female partner who becomes pregnant while the male subject is in this trial. This applies only to male subjects who receive IMP.
- After obtaining the necessary signed informed consent from the pregnant female partner directly, the investigator will record pregnancy information on the appropriate form and submit it to the sponsor within 24 hours of learning of the partner's pregnancy. The female partner will also be followed to determine the outcome of the pregnancy. Information on the status of the mother and child will be forwarded to the sponsor. Generally, the follow-up will be no longer than 6 to 8 weeks following the estimated delivery date. Any termination of the pregnancy will be reported regardless of fetal status (presence or absence of anomalies) or indication for the procedure.

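### Partner pregnancies are collected only to Visit 17, about 28 days after the last dose, although men must use condoms for 94 days after it

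*Protocol*

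**What the plan says.** Four parts of the protocol bear on this point.

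- **Male contraception.** Section 5.1, criterion 2, applies to men whose partner is pregnant or of childbearing potential. They must use condoms while being treated and afterwards, "until the end of relevant systemic exposure in the male subject for 94 days following the last dose with IMP".
- **Collection period.** Section 8.4.5 says that details of pregnancies, including those in partners of male subjects, "will be collected after the start of IMP and until the final contact at Visit 17".
- **Appendix 4 (10.4).** The investigator is to seek information on "any male subject's female partner who becomes pregnant while the male subject is in this trial". Once a pregnancy is in scope, "The female partner will also be followed to determine the outcome of the pregnancy".
- **When the trial ends for a subject.** Section 4.1 states: "A Post-treatment Follow-up Visit will be made approximately 4 weeks after last dose of IMP". Section 4.4 counts a subject as completed after "all phases of the trial including the last scheduled procedure (ie, Visit 17 assessments". If no taper is used, section 7.3 says that "all assessments required at Visit 17 should be conducted approximately 30 days following the last dose".

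No contact after Visit 17 is scheduled in Table 3, and the SAP sets no longer collection period.

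**The concern.** Criterion 2 treats a man's exposure as relevant to a partner's pregnancy for 94 days after his last dose. Sections 8.4.5 and 10.4 stop looking for such pregnancies about a third of the way through that period. A pregnancy conceived in the remainder has no planned route into the record, and so none to outcome follow-up.

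Section 2.3 lists fetal toxicity among the important potential risks and relies on contraception and pregnancy testing to limit it. The scheduled tests are for female subjects. Partners are not tested, so for them a report is the only sign that contraception failed.

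The mismatch is specific to men. Female subjects must use contraception for 30 days after the last dose, which is within about 2 days of Visit 17.

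**Working it through.** **Inputs**

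- Taper: 3 weeks starting on Day 380 (Protocol 4.1, Table 4).
- Visit 17: Day 428 (Protocol 8.4.1, Table 3), with a ±3-day window; Visit 16 is Day 400, also ±3 days.
- Visit 17 without a taper: about 30 days after the last dose (Protocol 7.3).
- Condom period: 94 days after the last dose (Protocol 5.1).

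**Reproducing the plan's own interval**

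Last dose = 380 + 21 - 1 = Day 400. Last dose to Visit 17 = 428 - 400 = 28 days, which agrees with the roughly 4 weeks stated in 4.1.

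**Uncovered period**

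Uncovered days = 94 minus the days from last dose to Visit 17.

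| Case | Last dose to Visit 17 (days) | Uncovered days | Share of 94 days |
|---|---|---|---|
| Completer, nominal days | 28 | 66 | 70.2% |
| Visit 17 moves by ±3 days | 25 to 31 | 69 to 63 | 73.4% to 67.0% |
| Visits 16 and 17 both move by ±3 days | 22 to 34 | 72 to 60 | 76.6% to 63.8% |
| No taper | 30 | 64 | 68.1% |

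The third row assumes that the last dose moves with Visit 16. Table 4, note a, makes this possible, because enough drug is dispensed for subjects to stay on the existing dose until the next in-clinic visit.

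**Against the whole contraception period**

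For a completer, the male contraception period runs from Day 1 to Day 400 + 94 = Day 494. The uncovered part is 66/494 = 13.4% and the covered part is 428/494 = 86.6%. Matching the two periods would carry collection to about Day 494, which is 66/7 = 9.4 weeks after Visit 17.

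**Other routes into the record**

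- *Post-trial SAEs (8.4.1, 10.3.3).* Section 8.4.1 applies "if the investigator learns of any SAE, including a death, at any time after a subject has been discharged from the trial", and then only if the investigator considers the event reasonably related. Section 10.3.3 is likewise limited to SAEs judged related. Appendix 4 states, under female subjects, that pregnancy itself is not an AE or SAE.
- *Post-trial pregnancy-related SAEs (10.4).* This clause also sits under female subjects and does not mention partners.
- *24-hour notice of a reported pregnancy (8.4.5).* It has no date limit of its own, but it sends the investigator to 10.4, where partner pregnancies are limited to the time the man is in the trial.

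None of these provides for collecting a partner pregnancy conceived after Visit 17.

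**The case against.** The best opposing case has five parts.

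1. **Late events are not wholly lost.** Section 8.4.5 classes abnormal pregnancy outcomes, such as fetal death or a congenital anomaly, as SAEs, and 8.4.1 requires notification of a related SAE learned of after discharge. The outcomes that matter most for fetal toxicity therefore have a possible route. This stands in part. The route depends on the news reaching the investigator and on a judgement of relatedness. It gives no record of late pregnancies with a normal outcome, so it gives no denominator.

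2. **The 94 days may be only a precautionary margin.** The protocol does not explain the figure. Section 8.5 monitors an overdose until the drug is undetectable, for at least 3 days, which hints at a short persistence. The condom rule also covers men whose partner is already pregnant, so it is not purely a conception window. All of this is fair, and harm within the 66 days has not been shown. But criterion 2 ties the period to relevant systemic exposure. Either that is right and collection should match, or the period is too long and criterion 2 should change.

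3. **The 70% figure uses the narrower denominator.** This stands: the 13% figure belongs beside it. Men in the window are also required to use condoms, so the number of pregnancies may be very small.

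4. **The consent form may already ask men to report later pregnancies.** The consent pages are not in the text reviewed, so this cannot be excluded. Sections 8.4.5 and 10.4 would still need aligning.

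5. **No planned analysis changes.** Correct: pregnancy is not a listed endpoint. This is a gap in safety collection and does not affect any estimate.

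**Conclusion.** The concern holds. For a completer on nominal days, 66 of the 94 post-dose condom days (70%) fall after partner-pregnancy collection ends. The range is 60 to 72 days with the visit windows, and the figure is about 64 days without a taper. This is 13% of the whole male contraception period. A partner pregnancy that comes to light by Visit 17 is followed to outcome, so the loss is confined to the late window.

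The finding rests on the two periods not matching. It does not assume that the drug persists for 94 days. It does assume that sites apply the cut-off as written and that the consent form does not already extend reporting. The documents give neither the number of men with a relevant partner nor a pregnancy rate, so no count is offered. The sponsor should correct this; confidence in its practical importance is moderate.

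**What to change.** In 8.4.5 and in the male-subject part of 10.4, extend collection of partner pregnancies to 94 days after the man's last dose, or to whatever period the sponsor confirms. At Visit 17, instruct male subjects to report any partner pregnancy conceived up to that date, including one recognised later, and follow it to outcome under the existing 10.4 process. If the sponsor concludes that 94 days is longer than needed, shorten the period in criterion 2 instead so that the two agree.

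The cost is protocol wording and one line in the Visit 17 instructions, where birth control is already reviewed. No visit is added. There are two drawbacks. Reporting would remain passive, so some pregnancies would still be missed. The few late reports would each need the partner's consent and, once the electronic tool is closed, a paper or telephone route.

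A minor separate point concerns female subjects. Table 3 marks no urine pregnancy test at Visit 17, although 8.4.5 asks for at least monthly testing for the duration of the trial. Marking the test there would remove the doubt.
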